1.4.10 Statistical Analysis

Statistical analysis will be performed using Statistical Package for Social Sciences (IBM SPSS statistics for windows, version 28). Shapiro Wilk test will be used to test for normality of data. Descriptive statistics will be used to analyze patient's demographic data. To investigate the effect of physical therapist intervention on motor performance two-way mixed ANOVA will be performed. To investigate the effect of physical therapy intervention on neurodevelopment two-way mixed ANOVA will be performed. The level of significance will be set at a p-value < 0.05.

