1.3 Objectives

To investigate the effect of modified supporting play, exploration and early development (SPEEDI) on neuromotor performance in infants born preterm when the intervention is provided by the parents post discharge from Neonate Intensive Care Unit (NICU) compared to infants born preterm receiving standard care at 3 months of corrected age

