1.3.1 Specific objective

1. To compare the difference in motor performance between infants born preterm receiving modified supporting play, exploration and early development intervention (SPEEDI) and standard care at baseline, 1 month, 2 months and 3 months of corrected age.
2. To compare the difference in neurodevelopment between infants born preterm receiving modified supporting play, exploration and early development (SPEEDI) and standard care at baseline, 1 month, 2 months and 3 months of corrected age
3. To compare the compliance of parents with infants born preterm receiving modified supporting play, exploration and early development intervention (SPEEDI) and standard care.

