1.4.6 Variables

Independent variable

1. Groups: Intervention group and standard care group
2. Time: At baseline, 1, 2 and 3 months of corrected age

Dependent variable

1. Motor performance
2. Neurodevelopment
3. Compliance

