1.4.8 Measurement

Prior to the assessment of motor performance and neurodevelopment, demographic details such as gestational age, length of stay in the hospital and medical diagnosis will be recorded. The measurement will be taken at 40 weeks of post menstrual age, 1 month, 2 months and 3 months of corrected age by the research assistants who will be blinded to group assignment.

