The Phase I of the original version of SPEEDI consist of parent therapist collaborative sessions to understand infant cues, readiness for interaction, developmental support and stressors, ideas to promote interaction and development and watching the videos which is provided during the stay in NICU. However, this phase I intervention will be provided post discharge from the NICU at 40 weeks. The main objective of making parents watch these videos would be to help parents interact with their infant and perform the activities at home since most of the parents would be anxious and not know how to interact with their infant. The Phase II from the original version consisted of home visit to provide the intervention post discharge from NICU. It consists of therapist guiding the parents to perform play-based activities at home with their infants and these activities can be performed as a part of daily activities with their infants especially during feeding, bathing and changing diapers. There are 5 main activities which the parents must perform with their infant at home. The activities are broken down into three stages that become progressively challenging over time. For this study purpose the phase II intervention will be provided at the hospital where the parent will need to bring their infant to the hospital and the 5 main activities will be broken down into two stages. During the monthly visit the principal researcher will assess and decide the infant's ability to progress the activity from stage 1(easy) to Stage 2(hard). If the infant is found to be not ready to progress to the next stage, they will continue with the same activity. The primary caretaker will be given activity booklet which will contain pictures, simple text and log to record daily

activities. To perform the play- based activities the primary caretaker will be asked to use toy within their natural home environment since the intervention does not require any specific or sophisticated toys.

Intervention	40 weeks	1 month	2 months
Activities	
 • Watching videos to understand cue-based interaction with the infant. • Introduce the activities that the parent can complete at home to promote midline and tracking of toys and faces 	
 • Watching people and toy • Tummy time • Holding head up • Kicking • Toy play 	
 • Watching people and toy • Tummy time • Holding head up • Kicking • Toy play

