Duration	20 mins/day	20 mins/day	20 mins/day
Frequency	5 days /week	5 days /week	5 days /week

Figure 4: Intervention Program

Activity	Stage 1	Stage 2
Activity1 – Looking at people and toys (4 minutes)	
 • Looking at people with support in supine • In side lying and swaddled 	
 • Tracking of caregiver in supine.
Activity 2- Tummy time (4 minutes)	
 • Tummy time on the caregiver’s chest 	
 • Tummy time on the floor
Activity 3- Holding head up (4 minutes)	
 • Head control with help from caregiver. • Head control by swaddling the baby. 	
 • Head control with less support from caregiver, unswaddled.
Activity 4- Kicking (4 minutes)	
 • Kicking with swaddle to support to support the arms. 	
 • Kicking with arms and legs free to move with slight support under the hips.
Activity 5- Toy play (4 minutes)	
 • With use of external support to bring hands and legs in middle. 	
 • Toy play without external support and variety of position such as supine and side lying.

Figure 5: Activity Description

The intervention will be provided as an outpatient based at JDWNRH by the principal researcher. It will require the parents to come to the hospital every month for the assessments and interventions. The parents will be called every week to ensure that they have no problem with the activities until the infant is 3 months of corrected age. The principal researcher will review and assess if the parents are performing the intervention correctly with the infant during the monthly visit. The parents in the intervention group will be advised not to share the activities and any information related to the intervention to other parents of preterm infants whom they might know.

They will be given appointment for assessment at different day or time and the information regarding the enrollment will be kept confidential.

Standard care group

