1.4.9 Data Analysis

The researcher assistant who performed the randomization will register all neonatal data, discharge variables and the follow-up data, during the appointments. Motor performance of the infant will be assessed using TIMP at 40 weeks, 1 month, 2 months and 3 months of corrected age and neurodevelopment will be assessed using RNDA. Scores of TIMP items and items from RNDA will be transformed from categorical scale to a continuous scale. The Rasch Unidimensional Measurement Model (RUMM) will be used for this process. The number of sessions and amount of time spent performing the intervention will be recorded and analyzed. All the variables will have double data entry.

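### The only analysis stated for TIMP is a four-visit mixed ANOVA with no deciding term, and none of its omnibus terms estimates the 3-month group difference in the overall objective

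*Combined protocol and SAP*

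**What the plan says.** The overall objective (1.3) asks about neuromotor performance under modified SPEEDI "compared to infants born preterm receiving standard care at 3 months of corrected age". Specific objective 1 (1.3.1) is wider: motor performance under modified SPEEDI and "standard care at baseline, 1 month, 2 months and 3 months of corrected age".

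The stated analysis (1.4.10) is "To investigate the effect of physical therapist intervention on motor performance two-way mixed ANOVA will be performed", at p < 0.05. The Abstract names the same method and adds no detail. Section 1.4.6 gives the within-infant factor as "Time: At baseline, 1, 2 and 3 months of corrected age", so baseline is one level of the outcome and not a covariate.

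On timing, 1.4.8 states "The measurement will be taken at 40 weeks of post menstrual age, 1 month, 2 months and 3 months of corrected age", and 1.4.9 confirms the instrument: "Motor performance of the infant will be assessed using TIMP at 40 weeks, 1 month, 2 months and 3 months of corrected age". The 40-week visit is also where treatment begins (1.4.8.4): "However, this phase I intervention will be provided post discharge from the NICU at 40 weeks". Support for the home programme then continues, with parents "called every week to ensure that they have no problem with the activities until the infant is 3 months of corrected age".

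Sections 1.4.9 and 1.4.10 otherwise add only Rasch scaling, a Shapiro-Wilk test and descriptive demographics. The readable text names no deciding ANOVA term, simple effect, post-hoc contrast or adjustment for baseline TIMP.

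**The concern.** A two-way mixed ANOVA yields tests of group, time and group-by-time. The overall objective needs one quantity, the group difference at 3 months, which is the first visit after the whole supported programme.

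- The group term estimates the mean of four visit-specific differences. One of these is the baseline, where treatment cannot yet have acted, and two are part-way through the programme.
- The group-by-time term is a 3-df test of any change in the group difference over time. It gives no direction, size or interval at 3 months, and it can be significant when the 3-month difference is zero.

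The trial could therefore report a p-value for one of these terms and have no planned 3-month estimate with an interval. Because the plan does not say which term decides, that choice could be made after the data are seen.

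**Working it through.** **Inputs from the plan.** Section 1.4.5 gives d = 1.29 for the TIMP z-score (no time point stated), 22 infants, and 28 after 20% dropout. Section 1.4.6 gives two groups and four time levels. Section 1.4.10 gives alpha 0.05.

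**Assumptions.** The plan gives no effect profile or between-visit correlation. I take two-sided tests, equal SDs at all visits, d = 1.29 at 3 months, no true baseline difference, and correlation ρ = 0.3, 0.5 or 0.7 under compound symmetry (CS) or AR(1).

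**Reproducing the sample size.** For a two-sample t-test with n = 11 per arm, the non-centrality is 1.29 × √(11/2) = 3.03 on 20 df, giving 82.1% power. This is the smallest n reaching 80% (80% target assumed). Dropout: 22/0.80 = 27.5, rounded up to 28. So the stated N fits a single two-group comparison, which 1.4.10 never names.

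**Group term, linear build-up.** The differences are 0, 0.43, 0.86 and 1.29 SD. Their mean is 2.58/4 = 0.645 SD, half the 3-month effect. Under CS the non-centrality is (n/2) × 0.645² / [(1 + 3ρ)/4]. At ρ = 0.5 this is 5.5 × 0.416/0.625 = 3.66 on (1, 20) df, giving 44.5% power.

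**Group-by-time term.** The deviations from the mean are ±0.645 and ±0.215, with sum of squares 2 × (0.416 + 0.046) = 0.925. At ρ = 0.5 under CS the non-centrality is 5.5 × 0.925/0.5 = 10.2 on (3, 60) df, giving about 74% power.

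**All scenarios, linear build-up, 11 per arm.** Group term and t-test are exact; the rest are simulated with 40,000 trials per scenario (Monte Carlo SE at most 0.0025). Entries are for ρ = 0.3 / 0.5 / 0.7.

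| Quantity (%) | CS | AR(1) |
|---|---|---|
| Group term, power | 55 / 45 / 37 | 64 / 52 / 42 |
| Interaction, uncorrected, power | 58 / 74 / 93 | 48 / 57 / 72 |
| Interaction, Greenhouse-Geisser, power | 54 / 71 / 92 | 45 / 52 / 66 |
| 3-month t-test, power | 82 | 82 |
| 3-month ANCOVA on baseline, power | 84 / 90 / 97 | 80 / 80 / 85 |
| Exactly one of group and uncorrected interaction significant | 49 / 52 / 61 | 50 / 50 / 54 |

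**Other profiles and N.** With 14 per arm and linear build-up, the two terms disagree in 44–54% (CS) or 45–49% (AR(1)) of trials. If the effect is full from month 1 (11 per arm), they disagree in 30–38%. If a benefit fades to nothing (0, 1.29, 0.645, 0), the uncorrected interaction is still significant in 61–97% of trials, although there is no 3-month difference to find.

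**Type I error.** If either term could be called success, the null rejection rate is 8.8–9.2% with the Greenhouse-Geisser correction. The 3-month ANCOVA stays at 4.5–5.0%.

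**Chance baseline imbalance.** P(|difference| ≥ 0.5 SD) = 2 × [1 − Φ(0.5/√(2/11))] = 2 × [1 − Φ(1.17)] = 24%. A 0.5 SD imbalance shifts an unadjusted 3-month difference by 0.5 times the correlation of 40-week with 3-month TIMP. That is 0.15–0.35 SD under CS (ρ) and 0.01–0.17 SD under AR(1) (ρ³).

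**The case against.** The strongest reply is that the ANOVA is a proper analysis and already contains the 3-month cell means. A 3-month difference with its interval can be drawn from the same fit, and specific objective 1 commits to comparing the groups at that visit. That is right: the gap is pre-specification, not an inability to answer. But without it, whether a contrast is run, which one, and with what error control are all left until after the data are seen.

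Other points stand in part:

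- **Specific objective 1.** The four-visit layout fits it, but its visit-by-visit comparisons would need contrasts too. Treating the overall objective as the primary question is a judgement, though a natural one.
- **Disagreement rate.** Two tests of middling power will often disagree. The figure matters only if the terms could be treated as interchangeable, and about half applies to linear build-up, not every profile. With baseline as a time level, group-by-time is the natural treatment test, but the plan does not say so.
- **The 9% error rate.** It supposes an either-term rule that the plan neither states nor excludes.
- **Sphericity.** The uncorrected interaction is somewhat liberal under AR(1), so its power there is flattered. The corrected row shows by how much.
- **Baseline adjustment.** At low correlation it gains nothing: under AR(1) 0.3–0.5, ANCOVA has 80% power against 82% for the t-test, with mean interval half-widths of 0.90 and 0.88 SD.

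**Conclusion.** The concern holds. The overall objective fixes the comparison at 3 months, and the only analysis stated for TIMP has no omnibus term that estimates it. This follows from the text and needs none of the assumed numbers.

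The size does depend on assumptions. With 11 per arm, linear build-up to 1.29 SD and ρ of 0.3–0.7, the group term targets half the 3-month effect, and the two candidate terms disagree in 49–61% of trials. They disagree less often if the full effect is present from month 1. Section 1.4.5 does not say at which age d = 1.29 was observed, and 1.4.9 plans Rasch-transformed scores, so these figures are illustrative. That the 40-week assessment precedes the first session is inferred from 1.4.8 and 1.4.8.4.

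This is a cheap improvement, not a fault that invalidates the design. The essential part is naming the 3-month contrast with its interval; baseline adjustment is the recommended form of it.

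**What to change.** In 1.4.10, name the primary TIMP analysis: the group difference at 3 months corrected age, adjusted for 40-week TIMP, two-sided at 0.05, with a 95% confidence interval. Either ANCOVA or the 3-month contrast of a linear mixed model with baseline as a covariate would serve. Keep the mixed ANOVA and the 1- and 2-month comparisons as secondary, for specific objective 1. Do not test the baseline difference as a treatment effect.

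This takes two or three sentences, with no new visits or data and the same software. The costs are:

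- One degree of freedom goes to the covariate, with no power gain if 40-week and 3-month TIMP correlate weakly.
- If the effect is full from month 1 and correlation is low, the group term would have had more power: 88% against 83% for ANCOVA (CS 0.3), or 85–93% against 80% (AR(1) 0.3–0.5).
- The group and interaction terms lose confirmatory status.
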